Recruitment. Eligible participants will contact our study in response to 1) flyers posted in VA mental health, primary care, and alcohol and substance use treatment programs; 2) advertisements in print and web-based media; 3) referrals from VA primary care, SAMI, PTSD, and other psychiatry clinics and 4) from other research studies who's participants provided consent to contact. Following verbal consent, potential participants will undergo an initial screening that takes approximately 30-45 minutes to complete. The screening, used in the PI's current CSR&D merit study, is intended to detect clinically significant alcohol use and PTSD symptoms. It consists of screening items from the SCID [52] and the Posttraumatic Stress Disorder Checklist-5 [PCL-5; 53] for disorders that are part of the inclusion and exclusion criteria. Those who meet study criteria will attend an in-person interview where they will sign informed consent documents and take part in a baseline assessment (see measures in 9.8.). Following baseline assessment, participants will have the opportunity to meet with a research study therapist to talk about their goals for taking part in the study treatments and the pros and cons of taking part in the study. Following the session, participants who choose to proceed with study participation will be randomized to the intervention or control condition. Random permuted blocks will be used which ensure exactly equal treatment numbers at certain equally spaced points in the sequence of patient assignment. A computer-generated randomization sequence will be provided by our and held by [name] study pharmacist. *Randomization will be stratified by whether or not the participant is on a anti-relapse medication. It is expected that randomization will balance out severity of PTSD symptoms, severity of alcohol use, and functional impairment, and this will be assessed in analyses excluded.*

Women and Minorities

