- **Exploratory Aims:** First, we will explore the extent to which lower drinking and PTSD symptoms are associated with better functional outcomes. Analyses will build on the secondary analysis models, where functional impairment (WHODAS, WSAS) serve as the dependent outcome variables in GLMMs. The exploratory analysis measures of percent heavy drinking days (PHDD) and PTSD symptom severity (CAPS) will be added as time-varying covariates in separate GLMMs, to examine whether lower drinking and lower PTSD severity are associated with better functioning. We will also explore prospective or “lagged” effects for these time-varying covariates (PHDD /CAPS), to test temporal precedence as an indication of drinking/PTSD severity as potential mechanisms of improved functioning. Second, we will test the mediating effect of alcohol cravings and PTSD symptoms on the direct effect of the interventions on heavy drinking. Using the recommended analytic framework for multilevel mediation in interventions [91], separate HLMs will examine the “a” path (intervention effect on mediator) and “b” path (mediator effect on outcome). The mediated effect will be estimated using the product-of-coefficients approach and statistical significance estimated with 95% CI's via the bias-corrected bootstrap [92]. Third, we will test the mediating effect of change in cognitive functioning from baseline to mid-treatment on the strength of the direct effect of the intervention on PTSD symptoms and SUDs. The same analytic framework for testing statistical mediation will be used as described above.

Genetic Testing

- For each gene candidate we will conduct a 2 way repeated measures ANOVA on the data from the participants in the topiramate arm (approximately 74 participants), with genotype as a between subject factor and time (baseline, 2 mo, 5 mo and 8 mo) as a within subject factor. We predict that genotype will moderate change in CAPS scores over time as supported by a genotype X time interaction. The same analysis strategy will be used on the non-topiramate arm to determine if genotype affects overall treatment response, or only response specific to topiramate
- **Covariates:** ancestry, sex, medication status, and baseline CAPS scores. We will correct for multiple comparisons based on number of gene candidates tested as appropriate.

DNA Sampling

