- Subjects will be asked for a saliva sample for immediate storage using an Oragene salivary sample kit. Using this kit allows for DNA quality that is similar to that of blood (99% concordance for SNP and CNV assessments between salivary and blood samples using this storage method), unlike mouthwash or buccal swab samples. Mouthwash samples are also not ideal due to having alcohol content which is inappropriate for this participant group. We felt that an invasive blood draw was also unnecessary given the high quality DNA sampling allowed for by the Oragene Discover kit. We will determine genetic ancestry using a small panel of 41 multiplex ancestry informative markers. The genotypes from the ancestry markers will be used to determine continental ancestry to construct principal components to be included as covariates.

DNA extraction and genotyping

- We will utilize the VMRF CFAR genomics core and standard extraction from Oragene salivary samples and polymerase chain methods as previously described by (Kolassa et al. 2010; Valente et al. 2011a) for COMTval158met genotyping. Genotype frequencies will be tested

against Hardy Weinberger Equilibrium using Pearson's goodness of fit 2.

Power Analysis:

Using Gpower we calculated that a total N of 75 will give us 0.9 power to detect a small-moderate effect size ($f=0.4$) of genotype if the SNP is common (e.g. 25/50/25 ratio in general population) using a 2 way repeated measures ANOVA (gene with 2 levels and time with 4 levels). For a t-test comparing final outcome measures post treatment, we have 0.8 power to detect a $d=0.75$ effect size with this N

- Repository: We will also use these samples for future sequencing, methylation and Genome Wide Association Analysis and merge genotype data and diagnostic data with other VA and/or NIH studies to increase power to discover new genetic associations with PTSD and PTSD treatment response

fMRI

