10) Describe the characteristics of the proposed subject population. Include age, gender, ethnicity, and health status as appropriate. Provide inclusion and exclusion criteria as appropriate. Indicate the number of VASDHS participants to be studied. For multisite studies, also provide the total number of subjects from all sites. Indicate the estimated number of consented subjects that will fail the screening process, if any.

Protection of Human Subjects

1. Risks to the Subjects.

1.a. Human Subjects Involvement and Characteristics

The participants in this study will be 120 outpatient male and female Veterans (60 per treatment condition), ages 18 or older, with alcohol use disorder (AUD) and PTSD.

In order to ensure that our sample represents the diversity of comorbidity in Veterans with PTSD, exclusion criteria are minimized and include only those factors that contraindicate primary treatment for PTSD, prevent the Veteran from benefiting from the current program, or may interfere with the mechanisms under study.

Inclusion criteria are:

- 1) Veterans of the U.S. military and/or Reserve/National Guard members,
- 2) at least 18 years of age,
- 3) survivors of a psychological trauma meeting DSM-5 criterion A, and are at least one month post-trauma,
- 4) have current DSM-5 diagnoses of AUD and PTSD based on semi-structured diagnostic interviews,
- 5) have at least 20 days of heavy drinking (≥ 5 drinks/day for men and ≥ 4 drinks per day for women) in the last 90 days spent in a non-restricted environment and meet criteria for heavy drinking at least 4 days in the last 30 days prior to screening,
- 6) are not currently receiving trauma-focused psychotherapy,
- 7) are literate in English and intend to stay in the San Diego area during the study,
- 8) are willing to attend psychotherapy, medication, and assessment sessions,
- 9) trying or planning to try to cut down on or abstain from alcohol,
- 10) for females of childbearing potential, agree to use an approved form of contraception for the duration of the study, including hormonal contraceptives (e.g., oral contraceptives or implantable devices), intrauterine device (IUD), or double barrier methods (e.g., diaphragm with spermicidal condom); barrier method is preferred as topiramate may make birth control less effective,

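### The exploratory genetic analysis assumes about 74 topiramate participants where the trial plans 60, uses month labels that do not fit the visit schedule, and has no test of whether a genotype effect is specific to topiramate

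*Combined protocol and SAP*

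**What the plan says.** All references are to the combined protocol and SAP.

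- **Arm size.** Section 9, Genetic Testing, plans a repeated-measures ANOVA for each candidate gene "on the data from the participants in the topiramate arm (approximately 74 participants"), with CAPS as the outcome. Section 10 gives "120 outpatient male and female Veterans (60 per treatment condition"). Section 9, Recruitment, says "Random permuted blocks will be used which ensure exactly equal treatment numbers at certain equally spaced points". Saliva is requested, not required: "Subjects will be asked for a saliva sample for immediate storage".
- **Power.** The genetic power analysis in Section 9 says "Using Gpower we calculated that a total N of 75 will give us 0.9 power to detect a small-moderate effect size" (f = 0.4) "if the SNP is common (e.g. 25/50/25 ratio in general population"), for a "2 way repeated measures ANOVA (gene with 2 levels and time with 4 levels"). It adds: "For a t-test comparing final outcome measures post treatment, we have 0.8 power to detect a" standardised difference of d = 0.75 at the same N. No alpha is given, nor which genotypes are merged to make two levels.
- **Time factor.** Genetic Testing uses baseline and months 2, 5 and 8. Section 9, Design, gives 16 weeks of treatment, with outcomes at baseline, post-treatment, and 3 and 6 months after treatment ends. The COVID-19 Procedures in Section 9 also mention a mid-treatment assessment.
- **Specificity.** Section 7 (the part on the saliva sample) asks whether genes moderate the topiramate effect. Genetic Testing answers this by repeating the same ANOVA in the other arm. It names no genotype-by-treatment term.
- **Status.** Section 6 lists the genetic question with the exploratory aims.

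**The concern.** Three things do not fit together. The analysis counts more topiramate participants than the design can supply, and the power figures appear to rest on that count. The month labels leave an analyst unsure which CAPS assessments enter the model. The rule for calling an effect specific to topiramate compares two separate within-arm results. A genotype effect that is equal in both arms can reach significance in one and miss it in the other, and could then be reported as a drug-specific finding. DNA is collected for this question, so a false pharmacogenetic claim is the main risk.

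**Working it through.** **1. Count.** 74 per arm under equal allocation needs 2 x 74 = 148 randomised; the plan is 120. 74/60 = 1.23, so the analysis assumes 23% more than the planned arm.

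**2. t-test power.** Inputs from the plan: d = 0.75, N = 75, genotypes 25/50/25, two gene levels. Merging the middle genotype with either end gives 25/75. Assumed, because not stated: alpha 0.05, two-sided first.

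Noncentrality = d x sqrt(n1 x n2 / N), df = N - 2.

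- N = 75 (18.75 v 56.25): 0.75 x sqrt(14.06) = 2.81; critical t 1.993; power **0.793**. This reproduces the stated 0.8.
- N = 60 (15 v 45): 0.75 x sqrt(11.25) = 2.52; critical t 2.002; power **0.696**.

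| Split | N = 75 two-sided | N = 60 two-sided | N = 75 one-sided | N = 60 one-sided |
|---|---|---|---|---|
| 25/75 | 0.793 | 0.696 | 0.873 | 0.800 |
| 1/3 v 2/3 | 0.856 | 0.768 | 0.917 | 0.856 |
| 50/50 | 0.893 | 0.815 | 0.942 | 0.890 |

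Of the six settings, only two-sided 25/75 returns the plan's 0.8 at N = 75. Power falls by 0.05 to 0.10 in every setting, before the planned multiplicity correction. In the two-sided 25/75 setting, the difference detectable with 80% power rises from d = 0.76 to d = 0.85.

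**3. ANOVA power.** Two groups, four times, f = 0.4, alpha 0.05 assumed, within-person correlation rho not stated.

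- Between-genotype test: lambda = N x f² x 4 / (1 + 3 rho). At N = 60 and rho = 0.5, lambda = 38.4 / 2.5 = 15.4 and power is 0.97. At rho = 0.7 power is 0.93. It drops below 0.90 only above rho of about 0.84, and is 0.86 at rho = 1.
- Genotype-by-time test, if f = 0.4 is defined for that term: lambda = N x f² x 4 / (1 - rho), at least 38.4 at N = 60, and power is above 0.99.

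**4. Visits, in months from treatment start.** Post-treatment: 16 x 7 / 30.44 = 3.7. The follow-ups fall at 6.7 and 9.7. Mid-treatment (week 8): 8 x 7 / 30.44 = 1.8. Month 2 could therefore be the mid-treatment visit. Month 5 lies 1.3 months after post-treatment and 1.7 before the first follow-up. Month 8 lies 1.3 after the first follow-up and 1.7 before the second. Neither matches a visit.

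**5. Specificity.** Let the true genotype effect be the same in both arms and each within-arm test have power p. The arms are independent, so the chance of significance on topiramate only is p(1 - p): 0.25 at p = 0.50 (the maximum), 0.21 at p = 0.70, 0.09 at p = 0.90, about 0.03 at p = 0.97, and below 0.01 when p exceeds 0.99. A direct interaction test at the 5% level gives a false difference 5% of the time, whatever p is.

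**6. What the direct test can detect.** Single-visit approximation, 60 per arm, a 0.75 SD difference between arms in the genotype effect, two-sided 0.05. SE = sqrt(2 x (1/n1 + 1/n2)), with n1 and n2 the genotype groups in one arm. For 15 v 45, SE = 0.422, ratio 1.78, power 0.42. For 20 v 40, power is 0.48. For 30 v 30, SE = 0.365, ratio 2.05, power 0.53.

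**The case against.** - **N = 75 is not tied to an arm by name.** This stands as a caution: the plan calls it a total N, and 75 genotyped people out of 120 is attainable. But it is one away from the 74 given for the topiramate arm, and the ANOVA being powered has the form of the within-arm one. Reading it as that arm is a sound inference, not a stated fact. The 74 itself contradicts 60 on any reading.
- **A reader might infer that power is simply 0.70.** The text does not support that without assumptions. Four of the six settings still reach 0.80 at N = 60, and neither alpha nor sidedness is stated. The genotype split is only partly open, since 25/50/25 with two levels points to 25/75.
- **A reader might infer that a false topiramate-specific result arises about 21% of the time.** That figure belongs to a single-visit t-test at power 0.70. The planned test is genotype by time in a repeated-measures ANOVA, and at f = 0.4 with power near 1 the rate is small. It rises with smaller effects or a stricter multiplicity-corrected alpha, to at most 25%. The plan also states no formal decision rule. The logical gap remains: two within-arm results are not a test of a difference.
- **A reader might infer that months 2, 5 and 8 are the post-treatment, 3- and 6-month visits mislabelled.** The three-month spacing suggests this, but month 2 also fits the mid-treatment assessment, so the intended visits cannot be settled from the text.
- **The analysis is exploratory.** That is true, and it limits the weight of the point.

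**Conclusion.** The concern holds. The count of about 74 contradicts the planned 60 per condition. The stated t-test power of 0.8 for d = 0.75 becomes about 0.70 at N = 60 with a 25/75 split and two-sided 0.05, and 0.77 to 0.89 under the other settings tried. These are best cases, before missing saliva and multiplicity correction. The 0.9 ANOVA power is not seriously threatened by the smaller N. The time factor does not fit the schedule, because months 5 and 8 match no visit. The specificity question has no valid test as written; the resulting error depends on per-arm power and cannot be fixed at one figure. The aim is exploratory, and the primary and secondary aims are unaffected.

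**What to change.** 1. State the topiramate N as at most 60, less those without a saliva sample.
2. Restate the t-test power for that N, giving alpha, sidedness, the genotype merge and the resulting split, before and after multiplicity correction. Say which ANOVA effect f = 0.4 refers to and what within-person correlation was used.
3. Reconcile the time factor with the visits in Design and in the COVID-19 Procedures, and name the CAPS assessments that enter the model.
4. Test specificity with the genotype x treatment x time term in one model on all genotyped participants, labelled exploratory. Report the within-arm ANOVAs as descriptive only.

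The cost is a change of wording in the analysis plan, plus a less favourable power statement. The interaction test will be weak: about 0.42 to 0.53 power for a 0.75 SD difference (single-visit approximation). A non-significant interaction should therefore not be read as evidence that the genotype effect is the same in both arms.

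### Genotype analysis: baseline CAPS is both an outcome level and a covariate, so the adjustment either drops out of the genotype-by-time test or breaks its sphericity assumption

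*Combined protocol and SAP*

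**What the plan says.** Section 9, Genetic Testing, plans for each candidate gene a "2 way repeated measures ANOVA on the data from the participants in the topiramate arm (approximately 74 participants"). Baseline is one of the four levels of the repeated factor, since the model is set up "with genotype as a between subject factor and time (baseline, 2 mo, 5 mo and 8 mo) as a within subject factor". The outcome and test come after that: "We predict that genotype will moderate change in CAPS scores over time as supported by a genotype X time interaction". The same analysis is to be repeated in the other arm. The next bullet gives the covariates as "ancestry, sex, medication status, and baseline CAPS scores", with a correction for the number of genes.

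The plan does not say whether covariates enter as main effects only or also crossed with time. It does not say whether the interaction is tested univariately or multivariately. The power paragraph that follows claims that a "total N of 75 will give us 0.9 power to detect a small-moderate effect size ($f=0.4$) of genotype". It limits this claim to a common variant with genotype shares of 25/50/25. It mentions no covariate, so it does not settle the model.

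**The concern.** The list of covariates suggests that the gene-response test is adjusted for starting severity. Because baseline CAPS is also a level of the outcome, whether that happens depends on a software choice that the plan leaves open. The possible fits give different p-values from the same data, for every gene. Under some of them a real association is more likely to be missed, in a small arm and before the multiple-gene correction lowers power further.

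**Working it through.** **1. The plan's own power figures.** Inputs from the power paragraph: N = 75, f = 0.4, two genotype levels, m = 4 times. Alpha is not stated for this test; I take 0.05. Visit correlation ρ is not given.
- Between-subject genotype effect: λ = f²Nm/(1+(m−1)ρ). At ρ = 0.5, λ = 0.16×75×4/2.5 = 19.2 and power is 0.991. It is still 0.928 as ρ approaches 1.
- Interaction: λ = f²Nm/(1−ρ) = 48/0.5 = 96 at ρ = 0.5, power about 1.00.

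So the stated 0.9 does not reproduce from the stated inputs. The companion t-test figure (d = 0.75, power 0.8) does: a 19:56 split gives 0.796. Neither calculation shows how baseline enters.

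**2. Baseline as a main effect.** Write CAPS for person i at time j as Y_ij = μ_j + δ_j g_i + βb_i + e_ij, where g is genotype and b is baseline CAPS. The term βb_i is the same at every time, so it cancels from any within-person contrast such as Y_ij − Y_i0. The genotype-by-time test is then an unadjusted comparison of change.

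The lost precision shows in the mean of the three post-baseline visits (SD 1, equal correlation):
- variance of change = 1 + (1+2ρ)/3 − 2ρ
- baseline-adjusted variance = (1+2ρ)/3 − ρ²
- at ρ = 0.5: 0.667 and 0.417, ratio 0.625
- ratios at ρ = 0.3, 0.7 and 0.8: 0.475, 0.775 and 0.85

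**3. Baseline crossed with time.** β now varies with j. At j = 0 the model regresses b on itself, so the slope is 1, the genotype term is 0 and every residual is 0. One of the four residual variances is exactly zero, so sphericity fails. The univariate test needs a correction. The multivariate test does not assume sphericity.

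**4. Power by simulation.** Assumptions: complete data, SD 1, equal correlation between visits, two-sided alpha 0.05, and genotype unrelated to baseline. Genotype is collapsed to 25% against 75%, which is an assumption. N = 60 comes from Section 10: "120 outpatient male and female Veterans (60 per treatment condition"). The effect is 0.6 SD at all three post-baseline visits.

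| ρ | Main-effect fit | Baseline-adjusted joint test, 3 df | Difference (points) |
|---|---|---|---|
| 0.3 | 37% | 69% | 32 |
| 0.5 | 50% | 69% | 19 |
| 0.7 | 73% | 83% | 10 |
| 0.8 | 90% | 93% | 3 |

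At ρ = 0.5 the crossed fit with a Greenhouse-Geisser correction has about 56%. The crossed fit tested multivariately equals the joint test in every setting. With N = 75 split 19:56 and a 0.5 SD effect, the main-effect fit has 33/47/69/87% and the joint test 62/66/78/91%, a loss of 29/19/9/4 points. Type I error was 4% to 6% in all fits.

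**5. Other effect shapes and tests.**
- Effect at the last visit only (N = 75, 19:56, 0.75 SD, ρ = 0.5): main-effect fit 83%, joint test 84%, one-df test on the post-baseline mean 30%.
- Baseline dropped from the time factor but genotype-by-time kept over the remaining visits: about 5% for a constant effect, which is no better than chance.

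**6. Genotype related to baseline.** Suppose genotype carries a stable 0.5 SD CAPS difference at all four visits and no effect on change. The baseline-adjusted difference is 0.5 − ρ×0.5 = 0.25 SD at ρ = 0.5, not zero. With N = 60 split 15:45, the joint test rejects about 14% of the time, the averaged test about 22% and the main-effect fit about 4%.

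**The case against.** A reader might infer that the plan as written has far less power however it is fitted. The documents do not support that. They leave open a fit with baseline-by-time tested multivariately, which loses nothing. They give no visit correlation, and the like-for-like loss for the main-effect fit is only about 3 points at 0.8.

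A reader might also set the main-effect fit against a one-df test on the post-baseline mean (about 50% against 85% at correlation 0.5, N = 60) and call the whole gap the cost of the double use. About 19 of those 35 points come from baseline handling. The rest comes from changing the hypothesis, and the averaged test does badly when the effect is confined to one visit.

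The strongest defence concerns the question asked. The prediction is about change over time, and genotype is not randomised. An unadjusted change test is not misled by a gene that tracks stable severity, whereas a baseline-adjusted test can be. That stands. It is a reason to state which quantity is meant and to report the other, but it does not justify listing a covariate that then has no effect. It is also fair that this is an exploratory addition that touches no primary or secondary aim.

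**Conclusion.** The double use of baseline CAPS is in the text and nothing elsewhere resolves it. That the adjustment vanishes (main effect) or that sphericity fails (crossed, univariate) is algebra and needs no assumption. The size of the power loss does need assumptions. For a constant 0.6 SD effect with N = 60 it runs from about 32 points at visit correlation 0.3 to about 3 at 0.8. It is nil for the crossed multivariate fit and nearly nil for an effect at the last visit only. Type I error is not inflated when genotype is unrelated to baseline. The point deserves correction before analysis, but it does not threaten the trial's main conclusions.

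**What to change.** In the Genetic Testing bullets, use baseline CAPS once. Since the plan already names it as a covariate:
- Take baseline out of the time factor and model CAPS at the three post-baseline visits, with baseline CAPS as a covariate.
- Test the genotype effect jointly across those visits (3 df). Do not keep genotype-by-time over the remaining visits as the test, because it would miss a constant effect.
- State how the other covariates enter.
- As a sensitivity analysis, report the unadjusted genotype-by-time change test, with baseline as an outcome level and removed from the covariates. Say that a result seen only in the adjusted test may reflect a stable severity difference.
- A one-df averaged test may be added, but is not a required replacement.

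The cost is a few sentences and one extra model per gene, with no new samples or data. The downside is the possible confusion of severity with response, which the sensitivity analysis is there to show.

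### The genetic power paragraph assumes 75 participants where the protocol plans 60 per arm; the t-test's 0.8 becomes 0.70 on the split that reproduces it, and lower after gene correction

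*Combined protocol and SAP*

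**What the plan says.** Section 9, Genetic Testing, plans one two-way repeated-measures ANOVA per candidate gene in the topiramate arm, which it puts at about 74 people. Genotype is the between-subject factor and time, at four points, is the within-subject factor. The predicted finding is a genotype-by-time interaction on the CAPS. On multiplicity it says: "We will correct for multiple comparisons based on number of gene candidates tested as appropriate". The number of genes is not given.

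The Power Analysis paragraph that follows makes two claims:

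- "Using Gpower we calculated that a total N of 75" participants "will give us 0.9 power to detect a small-moderate effect size". The effect is described as a "small-moderate effect size ($f=0.4$) of genotype", under the condition "if the SNP is common (e.g. 25/50/25 ratio in general population"), in a "2 way repeated measures ANOVA (gene with 2 levels and time with 4 levels").
- For a t-test on final outcomes, "we have 0.8 power to detect a $d=0.75$ effect size with this N".

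The paragraph gives no alpha, correlation between repeated measures, sphericity assumption, genotype group sizes or gene count.

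Section 10, item 1.a, says: "The participants in this study will be 120 outpatient male and female Veterans (60 per treatment condition"). Section 2, item 2a, gives the same total of 120. The Recruitment text in Section 9 uses permuted blocks to keep the arms equal.

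**The concern.** The sample size in the power paragraph cannot be met under the plan. With 120 randomized equally, the topiramate arm holds 60. Saliva is requested rather than guaranteed, so 60 is a ceiling. The power is therefore stated for a sample that the trial does not plan to have.

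Three further features make the paragraph hard to use. It powers an effect of genotype, while the hypothesis is genotype by time. It shows no allowance for the planned correction across genes. It also labels f=0.4 as small to moderate. A reader could conclude that modest genetic effects are detectable at 90% power, and that the post-treatment comparison has 80% power.

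**Working it through.** **Inputs from the documents.** N=75 (Power Analysis), about 74 (Genetic Testing), 60 per arm (Section 10); f=0.4; d=0.75; 2 genotype levels; m=4 times; genotype ratio 25/50/25.

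**Assumptions, because the documents are silent.** Two-sided alpha 0.05, or 0.05/g for g genes; correlation rho from 0 to 1. With two genotype levels, 25/50/25 collapses to 25/75 if carriers are pooled.

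**1. Planned arm size.** 120/2 = 60, against 74 or 75. The shortfall from 75 is 15, or 20%.

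**2. The t-test.** Noncentrality = d × √(n1·n2/(n1+n2)), with n1+n2−2 degrees of freedom.

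- Plan's figure, N=75 split 19/56: 0.75 × √(1064/75) = 2.825, df 73, critical t 1.993, power **0.796**. This reproduces the stated 0.8.
- N=75 in near-equal groups (37/38): power 0.893. This does not reproduce it, so an unequal split was probably used.
- N=60 split 15/45: 0.75 × √(675/60) = 2.516, df 58.
- N=60 split 30/30: 0.75 × √(900/60) = 2.905, df 58.

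| Genes (assumed) | Alpha | Critical t, df 58 | Power, 15/45 | Power, 30/30 |
|---|---|---|---|---|
| 1 | 0.05 | 2.002 | 0.70 | 0.815 |
| 3 | 0.0167 | 2.465 | 0.52 | 0.67 |
| 5 | 0.01 | 2.663 | 0.45 | 0.60 |
| 10 | 0.005 | 2.918 | 0.35 | 0.50 |

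**3. The ANOVA, read literally.** Two equal groups, N=75, f=0.4, alpha 0.05, univariate noncentral F.

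- Genotype: λ = f²·N·m/(1+(m−1)rho), df 1 and 73. The numerator is 0.16 × 75 × 4 = 48. At rho 0.5, λ=19.2 and power is 0.991; at 0.7, 0.973; at 0.9, 0.945; at rho 1, λ=12 and power is **0.928**, the minimum.
- Genotype by time: λ = f²·N·m·ε/(1−rho), df 3ε and 219ε. With sphericity (ε=1) power is above 0.999 at every rho from 0. At the lower bound ε=1/3 and rho 0, λ=16 and power is **0.976**, the minimum.

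Neither term gives 0.9.

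**4. Unstated settings that do give about 0.90, all for the genotype main effect at N=75.**

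- alpha 0.025 and rho 0.9: 0.903
- alpha 0.01 (five genes) and rho 0.7: 0.898
- three genotype groups and rho 0.88: 0.900
- a 25/75 split with d=0.8 (f = 0.8 × √(0.25 × 0.75) = 0.346) and rho about 0.78: 0.900

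**5. The ANOVA at N=60.** Genotype at alpha 0.05: 0.971 at rho 0.5 and 0.886 at rho 0.9. Genotype by time at rho 0: above 0.999 with sphericity and 0.940 at ε=1/3. At alpha 0.005 and rho 0 these become 0.997 and, with λ = 0.16 × 60 × 4/3 = 12.8 on 1 and 58 df, 0.74.

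**6. The label.** For two equal groups d = 2f = 0.8. That exceeds the d=0.75 in the next sentence. It also exceeds the top of the range (.140 to .623) that the trial's main power analysis cites for the drug effect on heavy drinking, although that is a different contrast. On a 25/75 split, f=0.4 corresponds to d = 0.4/0.433 = 0.92.

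**The case against.** The best defence is that the 0.9 misleads nobody into overconfidence: read literally, the design has more power than stated. The interaction, which is the term the hypothesis tests, stays near 1 at N=60 under sphericity even with ten genes. The t-test figure is also correct for its own inputs. The low corrected values depend on gene counts that the documents do not give, and on applying to the t-test a correction that the plan places with the per-gene ANOVA and qualifies by appropriateness. All of this stands. It limits the point to the sample size, the t-test figure, the missing inputs and the label.

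Three stronger readings are tempting but not supported:

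- **No correlation can give 0.9.** This holds only for two equal groups at alpha 0.05. The paragraph states neither, and the settings in step 4 reach 0.90. The three-group route conflicts with the stated two levels, but the others do not.
- **The calculation ignored the multiple-gene correction.** No alpha or gene count is given, and a corrected alpha is one route to 0.90. The documents show only that no allowance is visible.
- **The planned interaction test is underpowered.** At f=0.4 the univariate calculation does not show this except in extreme settings, such as ε=1/3, rho 0 and ten genes. Calling the 0.9 conservative does depend on that convention: a multivariate test at N=75 gives about 0.82, and setting λ = f²·N gives 0.83. The plan names an ANOVA.

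The total of 75 might also be read as spanning both arms. The Genetic Testing text analyses each arm separately and puts about 74 in the topiramate arm alone, so that reading does not fit.

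**Conclusion.** The point holds in limited form. The contradiction between 74/75 and 60 per arm needs no assumption. Its effect on the t-test is a fall from 0.80 to 0.70 at d=0.75, given the 25/75 split and alpha 0.05 that reproduce the plan's figure. With a Bonferroni correction for an assumed 3 to 10 genes, power is 0.52 to 0.35. If the groups were equal, 60 participants would still give 0.815 before correction, so the size of the loss depends on the split.

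The 0.9 cannot be verified. It is too low on the literal reading, attainable under unstated settings, and attached to genotype rather than to genotype by time. The small-to-moderate label does not fit f=0.4. Severity is minor: the genetic analysis is exploratory and bears on none of the three main aims.

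**What to change.** Rewrite the Power Analysis paragraph.

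- Reconcile 74 and 75 with 60 per arm, and allow for participants who give no saliva sample.
- State power for the genotype-by-time test and for the t-test at that number, at the alpha corrected for the stated number of candidate genes. Say whether the correction covers the t-test.
- Give the genotype grouping and split, the correlation, the sphericity assumption, and the effect-size convention used in the software.
- Remove the small-to-moderate label from f=0.4, and give the equivalent d for the assumed split.

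The cost is one recalculated paragraph, with no change to design or data collection. On the split that reproduces the plan's figure, the t-test result becomes less favourable. The interaction figure is likely to exceed 0.9 under most assumptions.
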